### **7.2.3 Secondary analyses in tumor tissue**

When remaining samples are available in sufficient quantity and quality, samples may be used to assess the mutational aberrations across a diverse patient population with newly diagnosed HR+ HER2- advanced breast cancer. This will be assessed based on baseline tumor tissue samples and compared across diverse races/ethnicities with HR+ HER2- advanced breast cancer.

**Table 7-2 Biomarker collection schedule**

Sample Type	Volume	Visit	Sample Collection
Baseline tumor biopsy (Fresh tissue from metastatic site preferred. If fresh tumor is not accessible, archival tissue will be accepted)	Blocks are preferred but if not possible, 20 unstained slides (minimum 15) should be made available.	Screening	Prior to treatment (or within the first month of study). If archival, can be sent in when obtained from sample storage.
Newly obtained post-progression tumor samples)	Blocks are preferred but if not possible, 20 unstained slides (minimum 15) should be made available.	Post- progression	Upon progression (prior to subsequent treatment)

## 8 Safety monitoring and reporting

### 8.1 Serious adverse events

For this companion sample collection protocol sample collection protocol, only serious adverse events considered related to the biomarker collection procedure will be extracted from the AE eCRF of the CLEE011A2404 protocol. All SAEs experienced should be reported in the CLEE011A2404 study EDC system, with a comment that the SAE was related to this US Companion sample collection protocol, protocol CLEE011AUS42.

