## 6.3 Concomitant medications

Concomitant medications and significant non-drug therapies given as treatment for serious adverse events considered by the investigator to be possibly related to the biopsy procedures will be collected as defined in the treatment protocol of main study CLEE011A2404 and documented in the treatment eCRF for CLEE011A2404 (ensuring to document in the eCRF details that this is related to US Companion sample collection protocol CLEE011AUS42).

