### 7.1.2 Patient data to be collected in the central laboratory requisition forms

Data for this companion sample collection protocol will be collected via the central laboratory requisition forms completed for each sample. These requisition forms will document that informed consent has been obtained for participation in this protocol and for storage of biological samples, confirm that the patient met the inclusion/exclusion criteria for CLEE011A2404, and collect information about the lesions biopsied at baseline and upon progression [REDACTED]. Any adverse events considered by the investigator to be related to the biopsy procedure, should be captured in the CLEE011A2404 study EDC database, with a comment that it is related to the US companion

sample collection protocol CLEE011AUS42. Additional data collected as part of the CLEE011A2404 protocol and needed for the interpretation of the results from the genomic analyses, will also be utilized.

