## **9.3 Data collection**

Biomarker (blood and tissue) samples drawn during the course of this companion sample collection protocol will be collected from the Investigator sites and analyzed by a Novartis assigned laboratory or contracted central lab. The results will be sent electronically to Novartis. Designated investigational site staff will complete the information required by the protocol into the appropriate central laboratory requisition forms (printed on 2 or 3-part non-carbon-required paper). Field monitors will review the central laboratory requisition forms for accuracy and completeness and instruct site personnel to make any required corrections or additions. One copy of the requisition form will be forwarded to each analytical laboratory

with the respective samples by the designated investigational site staff, and one copy will be retained at the investigational site.

The Principal Investigator is responsible for assuring that the data entered on the central laboratory requisition forms is complete, accurate, and that entry and updates are performed in a timely manner.

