### **10.4 Safety reporting**

#### **10.4.1 Serious adverse events (AEs)**

Summary tables for serious adverse events (AEs) have to include only AEs that are only suspected to be related to the biomarker collection procedures in the opinion of the investigator. Biomarker collection-related SAEs will be summarized by system organ class

[REDACTED]

and/or preferred term, severity (based on CTCAE grades) and type of serious adverse event. These will be reported in the CLEE011A2404 EDC system with a comment that the SAE is related to the companion sample collection protocol CLEE011AUS42 protocol.

Deaths reportable as SAEs and non-fatal serious adverse events will be listed by patient and tabulated by type of adverse event and treatment group.

Review of these safety data will be conducted on an on-going basis by members of the study team. The findings will be documented and will be made available upon request.

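### Sites must record non-serious biopsy-related adverse events for this protocol, but it extracts and summarises only the serious ones

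*Combined protocol and SAP*

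**What the plan says.** Three sections govern adverse events from the sampling procedures.

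- **Capture (Section 7.1.2).** "Any adverse events considered by the investigator to be related to the biopsy procedure, should be captured in the CLEE011A2404 study EDC database". Each such event is to carry a comment linking it to CLEE011AUS42. There is no seriousness threshold.
- **Extraction (Section 8.1).** For this protocol, "only serious adverse events considered related to the biomarker collection procedure will be extracted from the AE eCRF" of the parent study.
- **Reporting (Section 10.4.1).** "Biomarker collection-related SAEs will be summarized by system organ class" and/or preferred term, with CTCAE severity and type of event. For listings, "Deaths reportable as SAEs and non-fatal serious adverse events will be listed by patient". The ongoing review by the study team covers these same data.

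Section 10.4.1 is the only subsection of Section 10.4. Its opening sentence mixes two scopes: "Summary tables for serious adverse events (AEs) have to include only AEs that are only suspected to be related to the biomarker collection procedures". Section 6.3 follows the narrower scope, collecting concomitant treatment only when "given as treatment for serious adverse events considered by the investigator to be possibly related to the biopsy procedures".

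**The concern.** The protocol describes itself as not treatment-based and as leaving planned treatment unchanged, so the risk it adds comes from its sampling procedures. Fresh tissue is preferred at baseline, and the progression sample must be newly obtained. How often a study biopsy causes a complication of any grade is a natural safety question here.

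The capture rule would collect the data to answer it, but the extraction and reporting rules leave the non-serious part out. CTCAE grade is applied only within serious events. A related event of notable grade that does not meet the seriousness definition would therefore appear in no table or listing planned here. Sites would be annotating non-serious events for which this protocol states no analysis. Ethics committees and planners of later companion protocols would see the serious events but not the overall complication rate.

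**Working it through.** The plan states no figure to reproduce. The check compares three rules and then asks what size can be given.

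**1. The rules side by side**

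| Step | Section | Scope |
|---|---|---|
| Recorded and flagged | 7.1.2 | Any biopsy-related AE |
| Extracted for this protocol | 8.1 | Serious, procedure-related only |
| Summarised and listed | 10.4.1 | Serious only, though the opening sentence also says AEs |

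Non-serious biopsy-related events pass the first step and stop at the second. No other section extracts, tabulates or lists them.

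**2. Whether a later analysis plan closes the gap.** Sections 10 and 10.3 defer analysis details to stand-alone plans or the parent-study SAP. Section 8.1, however, restricts what is extracted in the first place. A later plan for this study that tabulated non-serious events would go beyond that restriction, so the change belongs in the protocol.

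**3. Size.** Let N be the biopsy-related events recorded and S the serious ones among them. The share left out is q = (N − S)/N = 1 − S/N. The documents give neither N nor S, so q can lie anywhere from 0 to 100%. As an illustration on assumed rates only, suppose 10–20% of biopsied patients have any related event and 1–2% have a serious one. The serious-only table would then show between 1/20 = 5% and 2/10 = 20% of affected patients. Neither input comes from the documents, so this range is not an estimate for this study.

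**4. Denominator.** A complication rate is patients with at least one biopsy-related event divided by patients with at least one fresh study biopsy. Two readily available denominators fail.

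- *All enrolled patients.* Table 7-2 says "If fresh tumor is not accessible, archival tissue will be accepted", so some patients may never have a study biopsy. If that fraction is a, the rate over all enrolled patients is (1 − a) times the rate among those biopsied.
- *The biomarker analysis set (Section 10.1).* It requires an evaluable biomarker result. It can therefore drop a patient harmed by a biopsy that gave no usable tissue, while keeping patients who supplied only archival tissue.

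**5. The identifying comment.** Section 8.1 can be read as asking for the comment on every SAE experienced, whereas Sections 8.1.1 and 8.1.2 flag only events suspected to be related. The comment identifies biopsy-related events reliably only once this is settled.

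**The case against.** The strongest reply is that serious-only reporting is a deliberate scope. Sections 6.3, 8.1, 8.1.1 and 10.4.1 all focus on serious events, the analyses are declared exploratory, and no visible objective concerns safety. The most consequential events still get 24-hour reporting, summaries, listings and ongoing review. This stands as a limit on importance. It does not remove the mismatch: if the narrow scope is intended, Section 7.1.2 asks sites to flag events with no stated use here.

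The existing data may also be less complete than Section 7.1.2 suggests. It is the only section that asks for the comment on non-serious events, so flagging may be patchy and a table could undercount. This stands too, and it is a reason to align the instructions before building the table.

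A reader might go further and infer any of the following, none of which the documents support.

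- *Most biopsy harm goes unreported.* That needs q above 50%. This is plausible but undocumented, and counting events is not the same as weighing harm.
- *The data are discarded, or appear in no parent-study table.* The events stay in the CLEE011A2404 database, and Section 9.1 says data from the two studies will be combined. The parent protocol and SAP are not available, so their tables cannot be ruled out. Equally, nothing here shows that those tables would separate US biopsy events from other events.
- *Biopsy is the only procedure.* Section 9.3 refers to "Biomarker (blood and tissue) samples drawn during the course of this companion sample collection protocol", parts of the schedule are redacted, and baseline tissue may be archival.

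**Conclusion.** The point holds as a mismatch between capture and reporting. This protocol has sites record all biopsy-related adverse events but plans to extract, summarise and list only the serious ones. That follows from the wording of Sections 7.1.2, 8.1 and 10.4.1 and rests on no assumed rate. Deferral to a later SAP does not cure it, because the restriction is in the protocol's own extraction rule.

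The number or share of events affected cannot be given. The conclusion covers what is planned under this protocol, not what the parent study may report. The gap leaves the mutation analyses untouched but limits what the study can say about the harm of its biopsies. Given the low cost, the change should be made.

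**What to change.** 1. Reconcile Sections 7.1.2, 8.1 and 10.4.1 so that every adverse event carrying the CLEE011AUS42 comment is extracted, whether serious or not.
2. In Section 10.4.1, tabulate these events by preferred term, CTCAE grade and seriousness, with the SAE table as a subset, and add a listing by patient.
3. Use patients who had a fresh study biopsy as the denominator. Do not use the biomarker analysis set, and do not count patients who supplied only archival tissue.
4. Correct the wording in Section 10.4.1 that labels serious adverse events as AEs, in the heading and the opening sentence, so that the scope of each table is clear.
5. State in Section 8.1 that the comment is for related events only, in line with Sections 8.1.1 and 8.1.2.

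The cost is a protocol clarification, one extra table and one extra listing from data sites are already told to enter, and manual review of comment text. The table may undercount non-serious events if sites flag them inconsistently, and the report should say so. No treatment or clinical rule changes.

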#### 8.1.1 Serious adverse event definitions

Serious adverse events (SAEs) are defined in the CLEE011A2404 protocol. Those serious adverse events considered by the investigator to be possibly related to a biomarker collection procedure performed as part of this protocol will be indicated as such in the AE eCRF in the CLEE011A2404 EDC system.

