#### 8.1.2 Serious adverse event reporting

SAEs will be collected and reported as described in the CLEE011A2404 protocol. If the event is suspected to be causally related to a biomarker collection procedure, as assessed by the investigator, it will be identified as such. SAEs will be followed until resolution or until clinically relevant improvement or stabilization. SAE collection ends 14 days after the last biomarker collection procedure.

Any SAEs experienced after this 14 day period should only be reported to Novartis if the investigator suspects a causal relationship to a biomarker collection procedure performed as part of this companion sample collection protocol. Recurrent episodes, complications, or progression of the initial SAE must be reported as follow-up to the original episode within 24 hours of the investigator receiving the follow-up information. An SAE occurring at a different time interval or otherwise considered completely unrelated to a previously reported one should be reported separately as a new event.

Information about all SAEs is collected and recorded on the Serious Adverse Event Report Form; all applicable sections of the form must be completed in order to provide a clinically thorough report. The investigator must assess and record the relationship of each SAE to the biomarker collection procedures, complete the SAE Report Form in English, and send the completed, signed form by fax within 24 hours to the oncology Novartis Drug Safety and Epidemiology (DS&E) department.

The telephone and telefax number of the contact persons in the local department of Drug Safety and Epidemiology (DS&E), specific to the site, are listed in the investigator folder provided to each site. The original copy of the SAE Report Form and the fax confirmation sheet must be kept with the case report form documentation at the study site.

Follow-up information is sent to the same contact(s) to which the original SAE Report Form was sent, using a new SAE Report Form stating that this is a follow-up to the previously reported SAE and giving the date of the original report. Each re-occurrence, complication, or progression of the original event should be reported as a follow-up to that event regardless of when it occurs. The follow-up information should describe whether the event has resolved or continues, if and how it was treated, and whether the patient continued or withdrew from study participation.

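### Section 8.1 tells sites to label all SAEs as related to the companion protocol, while every other section reserves that label for events the investigator links to the collection procedure

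*Combined protocol and SAP*

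**What the plan says.** Section 8.1 consists of two sentences. The first sets what this protocol takes from the parent database: "only serious adverse events considered related to the biomarker collection procedure will be extracted from the AE eCRF of the CLEE011A2404 protocol". The second tells sites what to enter there: "All SAEs experienced should be reported in the CLEE011A2404 study EDC system, with a comment that the SAE was related to this US Companion". The rest of that sentence identifies the companion protocol as CLEE011AUS42.

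The neighbouring sections treat the same label as conditional. Section 8.1.1 says which events are marked in the parent AE eCRF: "Those serious adverse events considered by the investigator to be possibly related to a biomarker collection procedure performed as part of this protocol". Section 8.1.2 says: "If the event is suspected to be causally related to a biomarker collection procedure, as assessed by the investigator, it will be identified as such". It also requires a causality judgement for every event on the SAE Report Form: "The investigator must assess and record the relationship of each SAE to the biomarker collection procedures". Section 10.4.1 says the summary tables are to "include only AEs that are only suspected to be related to the biomarker collection procedures in the opinion of the investigator".

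**The concern.** The second sentence of Section 8.1 takes in every SAE and attaches a statement of relatedness to each one. The first sentence needs related and unrelated events to be kept apart. Both cannot be followed as written.

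This is an instruction to sites, so the wording matters in practice. Under Section 8.1.2, SAE collection runs until 14 days after the last collection procedure, and Tables 7-1 and 7-2 place the last planned procedure at progression. The period can therefore cover the time on ribociclib and letrozole, when SAEs due to treatment or disease are to be expected. A literal reader would mark those events as related to a tissue collection that had nothing to do with them.

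Two things are at stake. One is the accuracy of causality records in the parent trial's database. The other is the summary of procedure-related SAEs, the safety summary that Section 10.4.1 specifies for this companion protocol.

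**Working it through.** The protocol states no figure on this point, so no arithmetic applies. The check is to set side by side each place that says which events are marked, extracted or tabulated.

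1. **Section 8.1, first sentence (extraction).** Conditional: only SAEs considered related to the collection procedure are extracted from the AE eCRF.
2. **Section 8.1, second sentence (comment).** Unconditional: all SAEs receive the comment.
3. **Section 7.1.2 (comment).** Conditional: "Any adverse events considered by the investigator to be related to the biopsy procedure, should be captured in the CLEE011A2404 study EDC database". The note attached to the entry names the companion protocol.
4. **Section 8.1.1 (mark in the AE eCRF).** Conditional on possible relatedness in the investigator's view.
5. **Section 8.1.2 (identification).** Conditional on a suspected causal link.
6. **Section 8.1.2 (SAE Report Form).** Causality is assessed for each SAE, which presupposes that some will be judged unrelated.
7. **Section 10.4.1 (tables and comment).** Conditional. The tables hold only suspected-related events. The comment instruction, "These will be reported in the CLEE011A2404 EDC system with a comment that the SAE is related to the companion sample collection protocol", directly follows a sentence about collection-related SAEs, so it refers to those.

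Item 2 is the only one without a condition. Items 3 and 7 matter most, because they give the same comment instruction and restrict it to related events. The strength of the relatedness wording varies between sections (considered, possibly, suspected), but all of them require the investigator to see a link.

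To see what follows from item 2, take one SAE that the investigator judges to be caused by the drug.

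- On the SAE Report Form (item 6) it is recorded as unrelated to the procedure.
- In the AE eCRF (item 4) it is not marked as procedure-related.
- Under item 2 it still carries a comment that it was related to CLEE011AUS42.

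The records for this event now disagree. Whether it reaches the summary depends on what the extraction selects on. If that is the investigator's relatedness assessment, the event is left out correctly. If it is the comment, the event is counted wrongly. Section 8.1 names the AE eCRF as the source but not the field, and Section 8.1.1 does not say how the mark is made.

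The protocol gives no SAE rate, no biopsy complication rate and no number of US patients; Section 10.5 declares a sample size calculation not applicable. The number of events that might be mislabelled cannot be derived.

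**The case against.** The strongest reply is that this is a drafting slip that a careful site would read correctly. The preceding sentence limits the subject to procedure-related SAEs. Sections 7.1.2 and 10.4.1 repeat the comment instruction for related events only, and Section 6.3 ties a similar annotation for concomitant medications to SAEs possibly related to biopsy. An investigator who has just recorded an event as unrelated would have to contradict that record to follow Section 8.1 literally. The extraction and the tables are also defined by assessed relatedness, and no passage says that the comment selects events.

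Much of this stands. The surrounding text does give sites a reason to read the sentence narrowly. The comment is also not the only marker, because Section 8.1.1 provides an indication in the AE eCRF and Section 8.1.2 provides causality on the SAE Report Form.

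It does not remove the contradiction. Section 8.1.2 uses the phrase all SAEs for the full set of events, related or not, so the literal reading has support in the text. The SAE Report Form is faxed to drug safety, whereas the extraction comes from the AE eCRF, so a correct form does not by itself correct the database entry.

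A reader might infer that the extraction would necessarily fill with unrelated events. The documents do not support that: sites would have to follow the literal sentence, and the extraction would have to use the comment. A reader might also infer that mislabelling would set off Health Authority queries and Investigator Notifications. Section 8.1.2 links these to an SAE thought to be related to the procedure, says only that they may be needed, and does not make an EDC comment the trigger.

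**Conclusion.** The instruction in Section 8.1 is wrong as written and should be corrected. It conflicts with the sentence before it and with Sections 7.1.2, 8.1.1, 8.1.2 and 10.4.1. Followed literally, it puts false statements of relatedness into the database from which this protocol's SAEs are drawn.

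Contamination of the summary is a possibility, not an established result. It rests on two assumptions that the documents neither confirm nor exclude: that some sites follow the literal sentence, and that the extraction or its programming uses the comment. Any inflation factor would have to be built on assumed rates, so none is given.

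The rule for the tables in Section 10.4.1 is sound in restricting them to suspected-related events. The mutation endpoints in Section 3 are not affected. This is an inconsistency of modest weight in a safety instruction to sites, and it is worth correcting because the remedy costs almost nothing.

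**What to change.** Reconcile the second sentence of Section 8.1 with Sections 7.1.2, 8.1.1, 8.1.2 and 10.4.1. Suitable wording would be:

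> SAEs are reported as the CLEE011A2404 protocol describes. The comment linking an SAE to CLEE011AUS42 is added only where the investigator suspects that a biomarker collection procedure caused it.

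State also that the extraction is based on the investigator's relatedness assessment in the AE eCRF, and name the field that holds it, so that the summary does not depend on a free comment.

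The cost is one amended sentence, a short statement of the extraction field, and a note to sites. No new data are needed.
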